## 1.2. Study Rationale/Purpose

CC-122 is a new investigational product that has a strong biological rationale for the treatment of subjects with advanced relapsed or refractory cancers, an unmet clinical need. Potential efficacy and toxicities associated with CC-122 have been evaluated in preclinical studies and ongoing phase 1 studies and provide the scientific rationale for starting clinical development of CC-122 in Japan.

This study is the first phase 1 study with this IP in Japan. The primary purpose is to evaluate the safety, tolerability, and pharmacokinetics (PK) of CC-122 in Japanese subjects with advanced solid tumors or NHL. Preliminary efficacy will be assessed as a secondary objective.

The selected starting dose of 2 mg on a 5 continuous days out of 7 days per week intermittent dosing in this study is approximately one-half of the intermittent dose levels (4 and 5 mg on a 5 continuous days out of 7 days per week intermittent dosing schedule) assessed in the ongoing phase 1 study, CC-122-ST-001. Observed toxicity at dose levels up to the MTD of 3 mg QD on a continuous dosing schedule and ongoing intermittent dosing schedules had been manageable and these dose levels were well tolerated in Western subjects, with fatigue, neutropenia, and diarrhea as the most common toxicities, and no DLTs being observed at these dose levels in the continuous dosing schedule.

Based on the mechanism of action of CC-122, and the observed PK and metabolism of the compound, as well as reports of no PK differences observed with other similar compounds, differences in exposure between Western and Japanese patients are not expected.

Dose levels from 2 mg QD have demonstrated pharmacodynamic effects, including decreased peripheral B cells, expansion of peripheral T cells, decreased expression of a CRBN-modulated substrate in both B and T cells, and enhanced cytokine expression. The proposed starting dose of 2 mg on a 5 continuous days out of 7 days per week intermittent dosing schedule is below the NTD of 3.5 mg QD and the MTD of 3.0 mg QD in CC-122-ST-001 and is expected to be associated with manageable toxicities that can be monitored. Thus, the selected starting dose for this study is considered appropriate based on the safety of CC-122 in the ongoing western study in subjects with advanced solid tumors and hematologic malignancies and is within the safety tolerance established in preclinical toxicology studies.

## **2. STUDY OBJECTIVES**

### **2.1. Primary Objectives**

The primary objectives of the study are:

- To determine the safety and tolerability of CC-122 when administered orally to adult Japanese subjects with advanced solid tumors or NHL and to define the MTD and/or recommended phase 2 dose (RP2D)
- To determine the plasma PK of CC-122 in Japanese subjects with advanced solid tumors or NHL

### **2.2. Secondary Objective**

The secondary objective of the study is:

- To make a preliminary assessment of the antitumor activity of CC-122

### **2.3. Exploratory Objectives**

The exploratory objectives of the study are:

- To evaluate the plasma PK of CC-122 formulated capsules and compare results to the plasma PK of CC-122 AIC
- To assess the tolerability of CC-122 formulated capsules
- [REDACTED]

### **3. STUDY ENDPOINTS**

#### **3.1. Primary Endpoint(s)**

The primary endpoints of this study are:

- The following safety endpoints: DLTs, MTD, evaluated using the National Cancer Institute Common Terminology Criteria for Adverse Events (NCI CTCAE) criteria version 4.03
- PK parameters:  $C_{max}$ , AUC,  $T_{max}$ ,  $t_{1/2}$ , CL/F, Vz/F and Accumulation Index of CC-122

#### **3.2. Secondary Endpoint(s)**

The secondary endpoint of this study is:

- Antitumor efficacy, determined by response rates in each tumor type using appropriate tumor response criteria, and duration of response

#### **3.3. Exploratory Endpoint(s)**

The exploratory endpoints of this study are:

- Differences in  $C_{max}$  and  $AUC_{inf}$  between CC-122 AIC and CC-122 formulated capsules
- Differences in rates of DLTs between formulations
- [REDACTED]

[figure not shown]

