As of 13 Jan 2016, in Part A the most common treatment-emergent adverse events (TEAEs) (occurring in  $\geq$  20% of subjects overall) were fatigue, which was experienced by 19 (55.9%) subjects; neutropenia, 11 (32.4%) subjects; constipation, 9 (26.5%) subjects; nausea, peripheral edema and asthenia, which occurred in 8 (23.5%) subjects each; and dyspnea and vomiting, 7 (20.6%) subjects each. The system organ class (SOC) categories for which adverse events (AEs) were most frequently reported ( $\geq$  50% of all subjects overall experienced an AE that is categorized in the respective SOC) were Gastrointestinal Disorders, with 70.6% of subjects experiencing an AE in this SOC; General Disorders and Administration Site Conditions, 67.6%; Infections and Infestations, 55.9%; and Blood and Lymphatic System Disorders, with 50.0%.

Other than decreases in white cell counts, no laboratory abnormalities showed clear treatment-related changes. ECG and left ventricular functioning monitoring were unremarkable. Seven subjects had sporadic, asymptomatic, mild troponin-T laboratory test elevations from baseline, with no associated cardiac findings, and no clear association with dose or treatment duration. The subjects continued on study treatment. Subject monitoring and troponin elevation analysis is ongoing.

Preliminary pharmacokinetic analysis of CC-122 administered to subjects with solid tumors and hematologic malignancies demonstrated that CC-122 was rapidly absorbed and eliminated with a mean terminal half-life ranging between 8.3 and 25.2 hours. Overall  $C_{max}$  and AUC increased in a linear, approximate dose proportional manner with dose after single and multiple doses. There was moderate drug accumulation (about 30% to 40%) following repeated daily dosing. In vitro studies indicate mean CC-122 plasma protein binding is approximately 38%.

The preliminary results for best overall tumor response in study CC-122-ST-001 included one complete response (CR), in a subject with follicular lymphoma in the 3 mg QD cohort, and two partial responses (PR), both in subjects with lymphoma (DLBCL and MCL) in the 3 and 3.5 mg cohorts.

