## 5. TABLE OF EVENTS

The following table lists all of the assessments and indicates with an “X” the visits when they are performed. More frequent examinations may be performed at the investigator’s discretion if medically indicated, and clinically significant results should be recorded on Unscheduled Visit case report forms (CRFs). All data obtained from these assessments must be supported in the subject’s source documentation.

After completion of Cycle 1, written informed consent will be obtained again from subjects prior to the start of the second cycle of treatment.

Subjects will be hospitalized during the DLT evaluation period (Cycle 1) as a rule.

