- b After completion of Cycle 1, written informed consent will be obtained again from subjects prior to the start of the second cycle of treatment.
- c As per the PPRMP, screening pregnancy tests must be performed within 10 to 14 days prior to starting dosing. FCBP with regular or no menstrual cycles will undergo postdose pregnancy tests as noted on this table, every week for the first 28 days and every 28 days thereafter until the end of treatment, and 28 days after the last dose of CC-122. However, FCBP with irregular menstrual cycles will undergo weekly assessments for the first 28 days, every 14 days thereafter until the end of treatment and the end of treatment pregnancy test must be performed 14 and 28 days after discontinuing treatment.
- d If screening assessments are performed within 2 days of Cycle 1 Day 1 these assessments do not need to be repeated on Cycle 1 Day 1.
- e Triplicate ECGs (3 recordings within  $2\pm 1$  minute intervals) will be performed only at screening. Single ECGs will be collected for all other visits.
- f During the study, LVEF assessments should be repeated on Day 1 after every three cycles starting with Cycle 3 and when clinically indicated (for example, for decreased cardiac output) using the same modality at screening.
- g Ophthalmology examinations will be performed for all subjects at screening and during the study if clinically indicated.
- h Tumor assessments include imaging studies (via CT/MRI) and may include brain scans, and/or bone marrow aspirate/biopsy depending on tumor type and involvement. After screening, tumor assessments will be performed on Day 15 of Cycle 2, 4, 6 and every 3 cycles thereafter (Cycles 9, 12, 15, etc.), with an allowable window of  $\pm 7$  days. Tumor assessments at the end of treatment visit may be omitted if performed within the previous 28 days.
- i Refer to Section 6.4 for details on PK sampling time points.
- j Starting from Cycle 1 Day 1, CC-122 is administered once a day for 5 continuous days out of 7 days per week.
- k If performed on Day 13, a dose of CC-122 will not be administered.

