**Table 7: PK Sampling Time Points**

Visit	Nominal time point	Allowable window
Cycle 1 Day 1	Predose	<15 min prior to dosing
	0.5 hours postdose	± 5 minutes
	0.75 hours postdose	± 5 minutes
	1 hour postdose	± 5 minutes
	1.5 hours postdose	± 5 minutes
	3 hours postdose	± 10 minutes
	5 hours postdose	± 10 minutes
	8 hours postdose	± 10 minutes
Cycle 1 Day 2	24 hours after dose administered on Cycle 1 Day 1 and predose of dosing on Cycle 1 Day 2	<15 min prior to dosing
Cycle 1 Day 10, 11 or 12	Predose	<15 min prior to dosing
	0.5 hours postdose	± 5 minutes
	0.75 hours postdose	± 5 minutes
	1 hour postdose	± 5 minutes
	1.5 hours postdose	± 5 minutes
	3 hours postdose	± 10 minutes
	5 hours postdose	± 10 minutes
	8 hours postdose	± 10 minutes
Cycle 1 Day 11, 12 or 13	24 hours after dose administered on Cycle 1 Day 10, 11 or 12 and predose of dosing on Cycle 1 Day 11, 12 or 13	± 1 hour

Should dose administration CC-122 be interrupted for > 72 hours before the Cycle 1 Day 10, 11 or 12 sampling, serial PK samples will not be collected until ≥ 2 days of CC-122 continuous treatment has been reestablished.

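### Both PK profiles stop at 24 hours, so about 14% to 52% of Day 1 AUCinf is extrapolated; the formulations should be compared on measured AUC

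*Combined protocol and SAP*

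**What the plan says.** Section 3.3 makes the exploratory formulation endpoint the differences in Cmax and AUCinf "between CC-122 AIC and CC-122 formulated capsules". Section 3.1 lists Cmax, AUC, Tmax, half-life, "CL/F, Vz/F and Accumulation Index of CC-122" as primary PK parameters.

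Table 7 (Section 6.4) takes samples predose and at 0.5, 0.75, 1, 1.5, 3, 5 and 8 hours, and then one more. On Day 1 the last sample falls "24 hours after dose administered on Cycle 1 Day 1 and predose of dosing on Cycle 1 Day 2". For the second profile it falls "24 hours after dose administered on Cycle 1 Day 10, 11 or 12 and predose of dosing on Cycle 1 Day 11, 12 or 13". Neither profile has a sample between 8 and 24 hours or after 24 hours.

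For study CC-122-ST-001, Section 1.1.3 reports a "mean terminal half-life ranging between 8.3 and 25.2 hours", and adds: "There was moderate drug accumulation (about 30% to 40%) following repeated daily dosing". The same section gives the healthy-subject crossover result (N = 18): AUCinf was 16.29% higher and Cmax 35.58% higher with the formulated capsule. The justification for amendment 02 cites both figures as the reason for studying the new capsule here.

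Cohort 4 has at least 6 subjects (Section 4.1) and each AIC level has 3 to 6 (Section 4.1.1). Section 10.3 says that the sample size has no statistical basis. The visible text of Section 10.9 names AUC without saying which one, plans descriptive statistics, and gives no rule on extrapolation.

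**The concern.** A 24-hour profile covers 24/8.3 = 2.9 half-lives at one end of the reported range but only 24/25.2 = 0.95 at the other. AUCinf adds to the measured area a tail equal to the last concentration divided by the terminal slope, and that slope rests on about three samples (5, 8 and 24 hours). The AUC chosen for the formulation comparison is thus the one that depends most on extrapolation. AUC0-24 and AUCtau are fully covered by samples already planned.

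Two things are at stake. The AUCinf comparison between cohorts of 3 to 6 and about 6 subjects carries measurement error that could be avoided. Half-life and Vz/F need the terminal slope on both sampling days, so two primary PK parameters for Japanese subjects become imprecise if elimination is slow.

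**Working it through.** The plan states no extrapolated fraction and no power for this comparison. The one figure that can be checked is the accumulation. Everything below assumes linear one-compartment decline, which the documents do not state.

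**1. Extrapolated share of Day 1 AUCinf.** Share beyond 24 h = 2^(−24/t½).

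- 8.3 h: 13.5%
- 12 h: 25.0%
- 25.2 h: 51.7%

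The share passes 20% when t½ exceeds 24·ln2/ln5 = 10.3 h, and 50% only when t½ exceeds 24 h.

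**2. Check against the stated accumulation.** With once-daily dosing R = 1/(1 − share), so share = 1 − 1/R.

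- R = 1.3: 23.1%, effective t½ 11.3 h
- R = 1.4: 28.6%, effective t½ 13.3 h

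Both half-lives lie inside 8.3 to 25.2 h, so the two figures in Section 1.1.3 agree. The ends of the half-life range would give R = 1.16 and 2.07.

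**3. Precision of the terminal slope.** For a log-linear fit, SD(λ) = σ/√Σ(t − t̄)², with σ the log-scale concentration error (assumed).

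- Samples at 5, 8, 24 h: Σ = 208.7. With σ = 0.15, SD(λ) = 0.0104 per hour.
- CV of λ: 12% at 8.3 h (λ = 0.0835), 18% at 12.3 h (λ = 0.0564), 38% at 25.2 h (λ = 0.0275).
- With σ = 0.10 these become 8%, 12% and 25%.
- Samples at 8, 24, 48, 72 h: Σ = 2352. With σ = 0.15, the CV at 25.2 h is 0.00309/0.0275 = 11%.

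**4. Error passed to AUC.** Simulation on the Table 7 times, with an assumed absorption rate of 2/h and the slope taken from the last three samples. CVs are from concentration error alone:

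| t½ | Concentration error | AUC0-24 | AUCinf |
|---|---|---|---|
| 8.3 h | 10% | 4.7% | 5.1% |
| 12.3 h | 10% | 4.9% | 7.5% |
| 25.2 h | 10% | 5.2% | 21% |
| 8.3 h | 20% | 9.4% | 10.5% |
| 12.3 h | 20% | 9.9% | 16.9% |
| 25.2 h | 20% | 10.5% | 60% |

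AUC0-24 is almost insensitive to half-life; AUCinf is not.

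**5. What limits the formulation comparison.** Two-sample t test on the log scale, two-sided 5%, effect ln(1.1629) = 0.151. Between-subject CV is assumed, 20% to 50%.

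- With perfect AUCinf, power is 22% to 8% at 6 versus 6, and 16% to 7% at 3 versus 6.
- At CV 30%, s = √ln(1.09) = 0.294 and SE = 0.294·√(2/6) = 0.170. The 95% limits are the ratio multiplied and divided by exp(2.228 × 0.170) = 1.46.
- Adding 10% AUCinf error lowers power from 12.7% to 11.9% (factor 1.49); adding 20% lowers it to 10.3% (factor 1.58).
- About 60 per group would be needed for 80% power at CV 30% (28 at CV 20%, 154 at CV 50%).

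**6. Is AUCtau near steady state on Days 10 to 12?** By superposition over the 5/7 schedule, AUCtau on day d as a share of steady state is (1 − r)·Σr^(d − j), summed over dosing days j up to d, with r = 2^(−24/t½). At 25.2 h (r = 0.517), Day 10 gives 0.483 × 1.858 = 90% and Day 12 gives 0.483 × 2.014 = 97%. So dose/AUCtau overstates CL/F by at most about 11% (1/0.90), and only at the slow end.

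**The case against.** The best defence is that the problem is usually moderate. The accumulation reported beside the half-life range implies an effective half-life of 11 to 13 hours and an extrapolated share below 30%. The 8.3 to 25.2 hours is a range of means, and Section 1.1.3 does not say how many lie near the top. At 12.3 hours with 10% concentration error, per-subject AUCinf error is 7.5%, or about 3% averaged over six subjects (7.5/√6). That is well below 16.29%. All of this stands, and it rules out saying that AUCinf is mostly extrapolated in general, or that its error always exceeds the effect sought.

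A reader might also infer that the sampling schedule is why a 16% difference cannot be seen. The documents do not support that: error-free AUCinf would still leave 8% to 22% power at 6 versus 6. Nor was Cohort 4 prompted by AUCinf alone. Cmax was 35.58% higher, is half of the endpoint, and needs no extrapolation.

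It is also fair to say that the endpoint is exploratory, the analysis descriptive, and no acceptance rule exists that a biased value could trip. The documents nowhere plan to drop subjects with high extrapolation. The unqualified AUC in Sections 3.1 and 10.9 already permits AUC0-24 and AUCtau. These points lower the stakes. They do not explain why Section 3.3 names the one AUC that the samples do not fully cover.

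Finally, later samples cannot repair the comparison. The justification for amendment 03 states that safety at the 2, 3 and 4 mg AIC levels has already been confirmed, so 72-hour profiles would come mainly from formulated-capsule subjects and the sampling would differ by formulation. This stands, and it is why late samples are only optional below.

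**Conclusion.** The point holds in a limited form. With sampling to 24 hours, about 14% to 52% of Day 1 AUCinf is extrapolated over the reported half-life range, and 23% to 29% on the reported accumulation. The cost is avoidable error in the AUCinf comparison. It is small near 8 hours and large near 25 hours, where the AUCinf CV is 21% against 5% for AUC0-24 at 10% concentration error. Half-life and Vz/F are imprecise when elimination is slow: the slope CV is 38% at 25.2 hours with 15% error.

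The inability to resolve 16% is mainly a matter of cohort size. Better AUC measurement improves the estimate but does not make the comparison conclusive.

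The extrapolated shares rest on one-compartment decline. The precision figures rest further on assumed concentration error, absorption rate and between-subject CV, none of which the documents give.

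**What to change.** 1. In Section 3.3, compare formulations on Cmax, Day 1 AUC0-24 and AUCtau from the second profile, reported as ratios with confidence intervals. Keep AUCinf as supportive only, with its extrapolated percentage listed for every subject.
2. In Section 10.9, say which AUC is computed from which profile, and take CL/F from dose/AUCtau of the second profile. State the sampling day used, since AUCtau is slightly short of steady state on Day 10 when half-life is long.
3. Report half-life and Vz/F with a caution that sampling ended at 24 hours.

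Items 1 to 3 need only wording, because the planned samples already supply the data in both formulations. The price is that AUC0-24 omits the tail and is less directly comparable with the healthy-subject AUCinf figure of 16.29%.

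4. Optional, for subjects still to be enrolled: take the second profile on Day 12 and add samples at 48 hours (Day 14) and 72 hours (before the Day 15 dose). These use the existing off-days. Table 3 notes of the 24-hour sample: "If performed on Day 13, a dose of CC-122 will not be administered". Section 5 adds: "Subjects will be hospitalized during the DLT evaluation period (Cycle 1) as a rule". No dose changes. At a 25.2-hour half-life the share beyond the last sample falls from 51.7% to 13.8%, and the slope CV from 38% to 11% at 15% error. Use these values for half-life and Vz/F only, not to compare formulations, because the AIC cohorts already reviewed have 24-hour profiles. The cost is two tubes per subject, no choice of sampling day, and the Day 15 dose waiting for the sample. The text should also say whether the added samples count toward the rule in Section 8.2.4 that replaces subjects missing more than 20% of PK samples.

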**Table 2: Provisional Dose-escalation Levels (Continued)**

Cohort	CC-122 dose
3	4.0 mg (5 continuous days out of 7 days per week intermittent dosing) AIC
4	3.0 mg (5 continuous days out of 7 days per week intermittent dosing) using the formulated capsules

The first dose level will be assessed in subjects with solid tumors or NHL, and subsequent dose levels will only be assessed in subjects with NHL.

After at least 3 subjects have been enrolled in the 4 mg CC-122 AIC cohort (Cohort 3) and this dose level is determined to be tolerable, at least 6 subjects will be subsequently enrolled in the 3 mg CC-122 formulated capsules cohort (Cohort 4) to evaluate for differences in PK and tolerability. Lower doses using CC-122 formulated capsules may be evaluated as necessary.

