#### **4.1.1. Evaluation of Dose-limiting Toxicities**

Cohorts of at least 3 subjects (to 6 subjects) will be enrolled at each dose level.

After the first dose is administered to the last subject in any cohort, subjects are observed for at least 28 days (Cycle 1) during the DLT evaluation period before the next higher, protocol-specified dose level cohort can begin.

A standard escalation schedule will be initiated in order to establish the MTD or RP2D by assessing the occurrence of DLTs. Smaller increments and additional subjects within a dose cohort may also be evaluated as necessary to determine the MTD and RP2D more precisely.

A dose level will be considered tolerable if 0 of 3 treated subjects experiences a DLT during the DLT evaluation period for each respective group. If 1 of 3 subjects experiences a DLT, 3 additional subjects will be enrolled and treated at that dose level.

A dose will be considered an NTD when two or more out of six evaluable subjects in a cohort experience DLTs during the DLT evaluation period.

The MTD is defined as the last dose level below the NTD with zero or one out of six evaluable subjects experiencing DLTs during the DLT evaluation period. At least 6 subjects will be enrolled at the MTD/RP2D.

The decision to either evaluate a higher dose level or declare the MTD or RP2D will be determined by the Safety Review Committee (SRC), which includes the principal investigator and Celgene's medical monitor (see Section 8.2.1), each time all clinical and laboratory safety data for a given cohort are available for review.

The SRC may decide to identify an RP2D based on safety, PK, and preliminary efficacy information, which will not exceed the MTD from global CC-122 trials in various indications.

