### 8.2.7. Criteria for Dose Escalation in the Next Cohort of Subjects

Cohorts will consist of at least 3 or at least 6 evaluable subjects. The decision criteria for dose escalation in any cohort are:

- If no DLT is observed in at least 3 evaluable subjects during the first cycle, the dose will be considered a well-tolerated dose and dose escalation will continue to the next dose level.
- If any DLT is observed in 2 or more of 6 evaluable subjects in the cohort, this dose is considered a non-tolerated dose and dose escalation will discontinue.

- If any DLT is observed in one evaluable subject during the DLT evaluation period, additional subjects will be enrolled to expand the cohort to up to at least 6 evaluable subjects.

The number of cohorts depends on the incidence of DLTs. A subject may experience more than one DLT. Dose-escalation decisions are based on the number of subjects experiencing DLTs.

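### The exploratory DLT-rate difference between formulations is biased on average against the formulated capsule, because the AIC cohorts must pass the 3+3 rule before the capsule cohort opens

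*Combined protocol and SAP*

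**What the plan says.** Section 2.3 sets an exploratory objective, "To assess the tolerability of CC-122 formulated capsules", and Section 3.3 pairs it with the endpoint "Differences in rates of DLTs between formulations". The text under Table 2 in Section 4.1 makes the capsule cohort conditional on the third AIC cohort: "and this dose level is determined to be tolerable, at least 6 subjects will be subsequently enrolled in the 3 mg CC-122 formulated capsules" cohort.

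The pass rule is in Sections 4.1.1 and 8.2.7:
- No DLT: "If no DLT is observed in at least 3 evaluable subjects during the first cycle, the dose will be considered a well-tolerated dose".
- One DLT: "If 1 of 3 subjects experiences a DLT, 3 additional subjects will be enrolled and treated at that dose level".
- Fail: "If any DLT is observed in 2 or more of 6 evaluable subjects in the cohort, this dose is considered a non-tolerated dose", and escalation stops.

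Reaching 4 mg AIC by this path therefore needs a pass at 2 mg and at 3 mg as well. The justification for protocol amendment 03 records that safety was confirmed at all three AIC levels; it gives no cohort sizes or DLT counts. Section 10 names no AIC comparator, estimator, interval or adjustment for the between-formulation DLT endpoint. Section 10.7 provides only summaries by dose level, cycle and tumor type.

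**The concern.** The comparator is chosen on the outcome being compared. At the moment it passes, an AIC cohort of nominal size can show only 0/3 or 1/6 DLTs, whatever its true rate. Cohort 4 can show any count. Two equally tolerable formulations would therefore give, on average, an apparent DLT excess for the capsule. Pooling AIC levels does not cure this, because each level passed the same gate.

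Section 1.1.3 says the capsule is the formulation selected for further development. It also reports 16.29% higher AUCinf and 35.58% higher Cmax for the capsule than for AIC in healthy subjects. A spurious excess would look plausible, and the crude difference cannot separate an exposure effect from the selection.

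**Working it through.** **Plan's own figure.** The only sample-size figure is approximately 15 subjects (Section 10.3, stated not to rest on a statistical calculation). The minimum cohort sizes reproduce it: 3 + 3 + 3 (Cohorts 1 to 3 with no DLT) + 6 (Cohort 4) = 15.

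**Inputs.** The pass and fail rules come from Sections 4.1.1 and 8.2.7, and the gate and Cohort 4 size from Section 4.1. The true Cycle 1 DLT rate p is an assumption, taken as equal in both formulations. The comparator is also an assumption, because the plan names none; I use the 3 mg AIC cohort (Cohort 2) and then all three AIC cohorts pooled.

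**Step 1: AIC cohort at its gate size.**
- P(pass) = (1−p)³ + 3p(1−p)⁵.
- E[AIC rate | pass] = (1/6) × 3p(1−p)⁵ / P(pass).
- At p = 0.10: P(pass) = 0.7290 + 0.1771 = 0.9061, and the expected rate is 0.0295 / 0.9061 = 3.3%.
- At p = 0.20: P(pass) = 0.5120 + 0.1966 = 0.7086, and the expected rate is 0.0328 / 0.7086 = 4.6%.

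**Step 2: Cohort 4.** With 6 subjects its expected rate is p, so the spurious excess is p − E[AIC rate | pass].

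**Step 3: AIC cohort expanded to 6 after passing at 0/3.** The three added subjects are not gated, so
- E[AIC rate | pass] = [(1−p)³ × p/2 + (1/6) × 3p(1−p)⁵] / P(pass).
- At p = 0.10: (0.0365 + 0.0295) / 0.9061 = 7.3%, an excess of 2.7 points.
- At p = 0.20: (0.0512 + 0.0328) / 0.7086 = 11.9%, an excess of 8.1 points.

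| Assumed p | AIC rate given pass | Excess v Cohort 2 at gate size | Excess v Cohorts 1–3 pooled, equal p | Excess v Cohort 2 expanded to 6 |
|---|---|---|---|---|
| 5% | 2.0% | +3.0 | +2.2 | +0.8 |
| 10% | 3.3% | +6.7 | +5.5 | +2.7 |
| 20% | 4.6% | +15.4 | +13.8 | +8.1 |

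Excess is in percentage points. A simulation at p = 0.20 gave +13.8 for the pooled case, as in the exact enumeration. If Cohort 4 stops once 2 of its first 3 subjects have DLTs, the excess over Cohort 2 at p = 0.20 rises to +17.9. The mean excess was positive in every scenario run.

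**Step 4: how often it would show.** Against Cohort 2 at gate size, the capsule rate is higher in 39.9% of trials and lower in 10.4% at p = 0.10, and 62.9% against 7.3% at p = 0.20. In an ungated 6 v 6 comparison with equal rates the two directions are equally likely: 29.1% each at p = 0.10 and 35.5% each at p = 0.20.

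**Step 5: imprecision.** Exact 95% intervals are 0 to 71% for 0/3 and 0 to 46% for 0/6. At p = 0.10 the SD of a rate in 6 subjects is √(0.10 × 0.90 / 6) = 12 points.

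**The case against.** The strongest reply is that the endpoint is exploratory, with no test, alpha or decision rule, and that the bias is modest at plausible rates. Section 1.1.3 reports no DLTs at 3 mg daily (n = 8), which is 3 × 7 = 21 mg a week against 3 × 5 = 15 mg on this schedule. Those subjects were outside this Japanese population, so p is not settled, but 5 to 10% is at least as defensible as 20%. There the excess over Cohort 2 at gate size is 0.03 × 6 ≈ 0.2 to 0.067 × 6 ≈ 0.4 of a subject, well inside the noise. This stands as a limit on size. It does not turn a biased contrast into a useful one.

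A reader might infer that the capsule will look more toxic in this trial. The documents do not support that. At p = 0.10 Cohort 4 shows 0/6 with probability 0.9⁶ = 0.53, and about half of trials tie against Cohort 2. At p = 0.05, with all AIC levels pooled and one expanded to 6, the mean excess is still +1.5 points, yet the capsule looks better slightly more often (30.5% v 26.3%).

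A reader might also infer that an AIC rate can never exceed 1/6. That holds only at the gate and for nominal cohort sizes. Section 4.1.1 allows additional subjects within a cohort and requires at least 6 at the MTD/RP2D, and Section 8.2.4 allows a spare subject per cohort. Subjects added after passing are not filtered and cut the bias by about half or more.

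Finally, the capsule's tolerability does not rest on this endpoint alone. DLTs are also a primary endpoint (Section 3.1), and Section 10.7 tabulates adverse events by dose level.

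**Conclusion.** The concern holds as a statement about average bias. The DLT-rate difference sets a comparator selected for few DLTs against an unselected cohort, and nothing in Section 10 corrects for it. With equal true rates of 5%, 10% and 20%, the expected spurious capsule excess over 3 mg AIC is about +3, +7 and +15 points at gate size, and about +1, +3 and +8 points if that cohort is expanded to 6 after passing. These sizes rest on the assumed p, on 3 mg AIC as comparator, and on Cohort 4 having 6 subjects. The pooled figures also assume the same rate at 2, 3 and 4 mg.

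A separate difference also stands in the way of reading the contrast as a formulation effect. By Sections 1.1.3 and 8.1, a 3 mg capsule is equivalent to 3.38 mg HCl, while 3 mg AIC is 3 mg HCl, so equal label dose is not equal drug content.

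No stated alpha or power is wrong, and the calculation does not call the MTD/RP2D decision into question: the Safety Review Committee makes it, and no rule ties it to this difference. The fault is in how the endpoint would be interpreted.

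**What to change.** In Section 3.3, replace the difference with: *DLT rate in evaluable Cohort 4 subjects, with exact 95% CI*. In Section 10.7 or the SAP, add that:
- AIC DLT counts and denominators are listed by dose beside it;
- the AIC levels were selected by the escalation rule, so their observed rates tend to be low;
- 3 mg capsule and 3 mg AIC differ in drug content (3.38 mg v 3 mg HCl);
- no between-formulation DLT inference is drawn from the crude difference.

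The cost is one changed line and a few sentences, with no new data, visits or subjects. The downside is that no formulation DLT difference is reported.

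A comparison of Cycle 1 neutrophil nadirs should not be required in its place. Febrile neutropenia and prolonged Grade 4 neutropenia are themselves DLT criteria (Table 8), so that measure is partly gated too. The data would also be few, non-randomised and sampled about weekly.
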